12.4 Analysis Datasets

Population	Definition
Enrolled	This will comprise all subjects who meet the eligibility criteria and are registered onto the study.

Population	Definition
Evaluable for Efficacy	This will comprise all subjects who receive at least one dose of sylvatron and pembrolizumab and either undergo at least one post-baseline assessment or die before any evaluation. Non evaluable patients will be replaced.
Intention-to-treat (ITT)	This will comprise all subjects who meet the eligibility criteria and are registered onto the study irrespective of their compliance to the planned course of treatment.
Per Protocol Set (Valid Cases, Efficacy Sample, Evaluable Subjects Sample)	This will comprise all subjects who complied with the protocol sufficiently to ensure that these data would be likely to exhibit the effects of treatment, according to the underlying scientific model. Compliance covers such considerations as exposure to treatment, availability of measurements and absence of major protocol violations. This population should be specifically defined in the protocol.
Safety	This will comprise all subjects who receive at least one dose of sylvatron and pembrolizumab
Treated	This will comprise all subjects who have been exposed to the planned course of treatment to any extent.

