2.1.2 Secondary Objectives

- Assess progression free survival of patients receiving pembrolizumab and Sylatron.
- Assess overall survival of patients receiving pembrolizumab and Sylatron
- Assess the objective response rate of patients receiving pembrolizumab and Sylatron combination therapy based irRECIST.
- Assess the safety and tolerability of combined pembrolizumab and Sylatron therapy.

Hypothesis:

We propose that a PFS of 24 weeks and an OS of 40 weeks is clinically meaningful in patients who receive the combination of pembrolizumab and Sylatron following failure on frontline therapy (due to cancer progression or intolerance of treatment).

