6.3 Subject Withdrawal/Protocol Therapy Discontinuation

Subjects may withdraw consent at any time for any reason or be dropped from the trial at the discretion of the site investigator should any untoward effect occur. In addition, a subject may be withdrawn by the site investigator or the sponsor-investigator if enrollment into the trial is inappropriate, the trial plan is violated, or for administrative and/or other safety reasons.

A subject must be discontinued from the trial for any of the following reasons:

- The subject or legal representative (such as a parent or legal guardian) withdraws consent.
- Confirmed radiographic disease progression
NOTE: A subject may be granted an exception to continue on treatment with confirmed radiographic progression if there is objective clinical benefit, please see Section 5.3
- Unacceptable adverse experienced
- Intercurrent illness that prevents further administration of treatment
- Site investigator's decision to withdraw the subject
- The subject has a confirmed positive serum pregnancy test
- Noncompliance with trial treatment or procedure requirements
- The subject is lost to follow-up
- Protocol therapy interrupted for > 12 weeks
- Completed 24 months of uninterrupted treatment with pembrolizumab or 35 administrations of pembrolizumab, whichever is later. **NOTE:** 24 months of pembrolizumab is calculated from the date of first dose.
- Administrative reasons

The End of Treatment and Follow-up visit procedures are listed in Section 7. After the end of treatment, each subject will have follow up visit (1) at 30 days after last dose of study treatment. Serious adverse events will be collected for 90 days after last dose of study treatment (follow up visit 2). Follow up for patients that have not experienced progression will occur every 9 weeks \pm 7 days. This may be done by phone call or other avenues as appropriate. Every effort should be made to obtain information on radiology scans or other types of disease assessment documentation. Once a subject experiences confirmed disease progression or starts a new anti-cancer therapy, the subject moves into the survival follow-up phase and should be contacted by telephone every 12 weeks \pm 7 days to assess for survival status until death, withdrawal of consent, or the end of the study, whichever occurs first.

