12.4.2 Analysis Plans for Secondary Objectives

Progression free survival (PFS) and overall survival (OS) will be evaluated using the methods of Kaplan and Meier (1958). 95% confidence interval will be constructed for the estimated median PFS and OS. The exploratory objective response rate will be estimated with its 95% exact confidence interval. Safety summaries will be presented by the severity of the adverse event and by relationship to study drug. Descriptive statistics (minimum, maximum, mean median, standard deviation for continuous variables; counts, percentages for categorical variables) will be used in summarizing of all laboratory and safety parameters (adverse events, serious adverse events, adverse events leading to discontinuation, deaths) for all treated subjects.

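### The Safety set requires a dose of both drugs, so patients who stop during the three-week Sylatron lead-in fall outside it, whereas Section 12.4.2 reports safety on all treated subjects.

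*Combined protocol and SAP*

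**What the plan says.** Under Section 5.2, Sylatron starts on Cycle 1 Day 1 and is given alone for three weeks. Pembrolizumab is first given at Week 4 (Cycle 2 Day 1).

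The table in Section 12.4 has two sets that bear on safety reporting:

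- The broader one, Treated, is worded: "This will comprise all subjects who have been exposed to the planned course of treatment to any extent".
- The narrower one, Safety, is worded: "This will comprise all subjects who receive at least one dose of sylvatron and pembrolizumab".

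The Evaluable for Efficacy row of the same table also requires a dose of both drugs, and adds: "Non evaluable patients will be replaced".

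Section 12.4.2 has two sentences on safety. The first names no population: "Safety summaries will be presented by the severity of the adverse event and by relationship to study drug". The second covers laboratory and safety parameters and does name one; its list ends "adverse events leading to discontinuation, deaths) for all treated subjects". No analysis in Section 12 is assigned to the Safety set.

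The secondary objective in Section 2.1.2 reads: "Assess the safety and tolerability of combined pembrolizumab and Sylatron therapy". Section 2.2.2 gives Grade 3 and 4 toxicities as the endpoint. Section 12.2.2 describes it more broadly, with adverse events, serious adverse events, those leading to discontinuation, and death.

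**The concern.** In a combination trial where both drugs start together, requiring both in the Safety set would seldom matter. Here every patient spends three weeks exposed to one drug only, and anyone who leaves in that time is outside the Safety set.

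The plan's own rules can produce such patients. Section 6.3 says "A subject must be discontinued from the trial for any of the following reasons", and the list includes "Unacceptable adverse experienced", intercurrent illness and withdrawal of consent. It makes no exception for the lead-in.

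The patients left out are not a random subset. Someone who stops for early Sylatron toxicity, or who dies before Cycle 2, is the kind of case the safety endpoint in Section 12.2.2 is meant to count. The event would have been collected, because Section 11.2.1 records adverse events from consent. If the tables were run on the Safety set, the event would still be missing from the reported toxicity, discontinuation and death rates.

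**Working it through.** **Reading the definitions side by side.** Take a patient who receives one or more Sylatron doses in Cycle 1 and stops before Cycle 2 Day 1.

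| Set (Section 12.4) | Requirement | Lead-in-only patient |
|---|---|---|
| Safety | a dose of Sylatron and of pembrolizumab | out |
| Evaluable for Efficacy | both drugs, plus a post-baseline assessment or death before any evaluation | out, and replaced |
| Treated | any exposure to the planned course | in |

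The lead-in is part of the planned course, so the Treated row includes this patient. The Evaluable for Efficacy row uses the same both-drugs condition, where it selects patients who reached the combination. That supports reading the condition literally in the Safety row.

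**The plan's headcount.** Section 12.3 allows 4% dropout on 44 patients: 44/(1 − 0.04) = 45.8, rounded up to 46. This reproduces the stated 46 and leaves room for 46 − 44 = 2 patients. The set definitions do not change this figure, nor the error rates of the two-stage design.

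**How many patients might be left out.** The documents give no lead-in stopping rate. Assume a rate q among 46 patients, independent between patients. The expected number outside the Safety set is 46q, and the chance of at least one is 1 − (1 − q)^46.

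| Assumed q | Expected number | Chance of at least one |
|---|---|---|
| 2% | 0.9 | 61% |
| 4% | 1.8 | 85% |
| 5% | 2.3 | 91% |
| 10% | 4.6 | 99% |

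**Effect on a reported rate.** Assume 44 patients receive both drugs and 10 of them have a Grade 3-4 event. Assume k further patients are lead-in-only and replaced, and that y of those k have an event (y from 0 to k).

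- Safety set rate = 10/44 = 22.7% for every k.
- Treated set rate = (10 + y)/(44 + k).

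| k | Treated, y = 0 | Treated, y = k | Safety minus Treated (points) |
|---|---|---|---|
| 1 | 10/45 = 22.2% | 11/45 = 24.4% | +0.5 to −1.7 |
| 2 | 10/46 = 21.7% | 12/46 = 26.1% | +1.0 to −3.4 |
| 5 | 10/49 = 20.4% | 15/49 = 30.6% | +2.3 to −7.9 |

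The k = 5 row needs 49 treated patients, more than the 46 planned, and is there only to show the range. The sign depends on whether the lead-in-only patients stopped with a severe event. If they did, the Safety set understates the rate. If they left for other reasons, it slightly overstates it.

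**The case against.** The strongest reply is that Section 12.4.2 already settles the matter. It assigns adverse events, serious adverse events, discontinuations and deaths to treated subjects, and the Treated row includes anyone exposed. On that reading the Safety row is an unused definition, and two differently defined sets do not contradict each other until one is used where the other is called for. The sentence on severity and relationship most naturally shares the population of the sentence after it. A both-drugs set may also be deliberate, since the objective concerns combined therapy. Finally, the event counts and stopping rates used here are all assumed.

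Much of this stands. Followed literally, Section 12.4.2 loses nobody, and the illustrative sizes are not forecasts. Three things remain:

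- The plan never says that Safety is a combination-only subset, and it gives that set no purpose.
- The sentence that would deliver Grade 3-4 counts names no set, so its population has to be inferred.
- A set called Safety is the one a programmer would expect to use for safety tables.

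As written, two different denominators can both be defended after the data are seen.

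**Conclusion.** The concern holds. As worded, the Safety set excludes patients exposed only in the Sylatron lead-in, and it is at odds with the population that Section 12.4.2 names for safety reporting.

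The effect is zero if the Treated set is used for every safety table. If the Safety set is used instead, the size is unknown. With two lead-in-only patients, in line with the plan's dropout allowance, and an assumed 10 events among 44, the Safety rate differs from the Treated rate by between +1.0 and −3.4 percentage points.

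The impact is modest and purely descriptive: the primary endpoint, sample size, error rates and stopping rule are untouched. It should still be corrected before analysis, because the patients at issue include those with early toxicity.

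**What to change.** 1. In Section 12.4, define Safety as all subjects who receive at least one dose of Sylatron or pembrolizumab, or merge the Safety and Treated rows, which would then be equivalent.
2. In Section 12.4.2, name that set for every safety summary, including the sentence on severity and relationship to study drug.
3. If safety during combined treatment is of separate interest, keep the both-drugs group as a supplementary set under its own label and say what it is used for.

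The cost is one word in the table and one set name in the text. Data collection does not change. Reported rates may move in either direction compared with tables run on the present Safety set.

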12.4.1 Analysis Plans for Primary Objective

The overall response rate will be estimated with its 95% exact confidence interval.

12.4.2 Analysis Plans for Secondary Objectives

Progression free survival (PFS) and overall survival (OS) will be evaluated using the methods of Kaplan and Meier (1958). 95% confidence interval will be constructed for the estimated median PFS and OS. The exploratory objective response rate will be estimated with its 95% exact confidence interval. Safety summaries will be presented by the severity of the adverse event and by relationship to study drug. Descriptive statistics (minimum, maximum, mean median, standard deviation for continuous variables; counts, percentages for categorical variables) will be used in summarizing of all laboratory and safety parameters (adverse events, serious adverse events, adverse events leading to discontinuation, deaths) for all treated subjects.

12.4.3 Analysis Plans for Exploratory Objectives

Density of CD3+ T cells and CD8+ T cells, proliferation of CD8+ T cells, Granzyme B+ cells and proliferation of tumor cells will be listed and summarized using the descriptive statistics (minimum, maximum, mean median, standard deviation). The CD8 + Tcells, Granzyme B+

cells, and proliferation of tumor cells will be correlated with the response by comparing the means of different groups using either 2-sample t-tests or non-parametric Wilcoxon rank-sum test, or the Chi-square test based on the distribution and structure of the data.

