2.1.3 Correlative/Exploratory Objectives

- Determine the effect of Sylatron on anti- programmed death ligand-1 (PD-L1) level, immune score as determined by the density of CD3 and CD8 in the tumor interior and invasive margin(s) of the tumor, and the clonality of the T-cell repertoire.
- Determine the effect of Sylatron on anti-cancer immunity by measuring proliferation of CD8+ T cells, Granzyme B+ cells and proliferation of tumor cells, and correlating these changes with clinical response as determined by RECIST 1.1.

Hypothesis:

Therapies that target the programmed death-1 (PD-1) receptor have shown unprecedented rates of durable clinical responses in a sub-group of patients with various cancer types [1-5]. Biomarkers in patient tumor that will predict response to anti-PD-1 therapy are being actively investigated. One mechanism by which cancer tissues limit the host immune response is via upregulation of PD-1 ligand (PD-L1) and its ligation to PD-1 on antigen-specific CD8+ T cells [6, 7]. Recent research has reported that tumor regression after therapeutic PD-1 blockade requires pre-existing CD8+ T cells that are negatively regulated by PD-1/PD-L1-mediated adaptive immune resistance [8]. We propose that Sylatron will increase the response of pembrolizumab by increasing the tumor infiltrating CD3 and CD8 cells, and the level of PD-L1 and PD-1 expression in immune cells and cancer cells. In this study, we will first test the effect of Sylatron on tumor infiltrating lymphocytes, the level of PD-1 and PD-L1 expression, and clonality of the T-cell repertoire by comparing the tumor biopsies from baseline and three weeks of Sylatron treatment. Then we will examine whether the change of tumor infiltrating lymphocytes, the level of PD-1 and PD-L1 expression from Sylatron treatment correlates with clinical response in patient treated with pembrolizumab and Sylatron combination therapy.

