8. BIOSPECIMEN STUDIES AND PROCEDURES

Biomarkers in patient tumors that can predict response to anti-PD-1 therapy are being actively investigated. One mechanism by which cancer tissues limit the host immune response is via upregulation of PD-1 ligand (PD-L1) and its ligation to PD-1 on antigen-specific CD8+ T cells [6, 7]. Recent research has reported that tumor regression after therapeutic PD-1 blockade requires pre-existing CD8+ T cells that are negatively regulated by PD-1/PD-L1-mediated adaptive immune resistance. [8] We propose that Sylatron will increase the response of pembrolizumab by increasing the tumor infiltrating CD3 and CD8 cells, and the level of PD-L1 and PD-1 expression in immune cells and cancer cells. In this study, we will first test the effect of Sylatron on tumor infiltrating lymphocytes, the level of PD-1 and PD-L1 expression, and clonality of the T-cell repertoire by comparing the tumor biopsies from baseline and three weeks of Sylatron treatment. Then we will correlate the change of PD-1, PD-L1 levels, immune score, and clonality of the T-cell repertoire from Sylatron treatment with clinical response.

Immunohistochemical (IHC) staining: The level of PD-1 and PD-L1 expression in tumor biopsy will be measured by immunohistochemical (IHC) staining at Merck laboratories. Immunohistochemical (IHC) staining, Digital image acquisition and analysis: The density of intratumoral total (CD3+) and cytotoxic (CD8+) T lymphocytes will be measured in the tumor interior (TI) and in the invasive margin (IM) of the three biopsied tumor samples. Immune cell densities will be obtained by immunohistochemistry and quantified using a biomarker imaging system in tandem with Image J processing software at Lombardi Comprehensive Cancer Center. Immune cell density in the TI and IM was converted to a binary score (0 as Low, 1 as High), with a cutoff threshold determined by the median density of CD3+ and CD8+ cells. We previously carried out a study on the association of intratumoral CD3 and CD8 cell density with recurrence free survival in patients with surgically resected Hepatocellular Carcinoma.

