8.1 Tumor Biopsies

Archival tissue will be requested for all subjects. All subjects will have a biopsy performed of a safely accessible tumor before starting treatment (within 42 days of starting treatment on this protocol) and 3 weeks later prior to initiation of pembrolizumab (prior to Cycle 2 Day 1). Subjects for whom newly obtained samples cannot be provided (e.g. inaccessible tumor for biopsy or subject safety concerns) may omit both biopsies provided documentation of reason is clear in the medical record. In these instances, submission of an archived specimen only will suffice.

Analysis of molecular characteristics of baseline and on-treatment tumor samples. All patients will have biopsies performed of safely accessible tumors before starting treatment (within 42 days of starting treatment on this protocol) and 3 weeks later. Preferred biopsy is core biopsy; five 20-gauge core needle biopsies (diameter about 2 mm) with a throw length of approximately 2 cm will provide adequate tissue for study. Available paraffin embedded tumor tissue from prior biopsies or excisions will also be collected as pre-treatment comparator samples. Preferred archival material includes tissue obtained in the same manner as specified in this trial and with no systemic anti-tumor treatment received by the patient between the biopsy and their enrollment on this protocol. However, other archival tissue may also be collected.

Each set of core biopsies will be divided into 5 portions and processed as below for later analysis:

- 1) FFPE for histology and IHC (20% of the specimen, or 1 core biopsy)
- 2) Quick-frozen in OCT for immunohistology and protein studies (40% of the specimen, or 2 core biopsy): embedded in optimum cutting temperature (OCT) solution, frozen in liquid nitrogen, and then stored at -80° C.
- 3) Placed in RNA-later for RNA and RT-PCR (40% of the specimen, or 2 core biopsy).

Of note, patients who are on chronic anticoagulation will be required to hold anticoagulation prior to the biopsies being performed. Patients on warfarin must hold treatment for 5 days, but will be on low-molecular weight heparin (LMWH), 1mg/kg subcutaneously twice a day. The LMWH will continue until the last biopsy is complete. Patients may then resume warfarin the day after the last biopsy. Additionally, patients on LMWH will hold (*i.e.*, not receive) the dose of LMWH the morning of the procedure, but will resume the LMWH the evening of the day of the biopsy.

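### The exploratory biopsy objective is a within-patient change, but section 12.4.3 specifies no analysis of that change and omits PD-1, PD-L1 and T-cell clonality

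*Combined protocol and SAP*

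**What the plan says.** Section 2.1.3 sets out two steps. In the first, "we will first test the effect of Sylatron on tumor infiltrating lymphocytes", on PD-1 and PD-L1 expression and on clonality, "by comparing the tumor biopsies from baseline and three weeks of Sylatron treatment". The second is "correlating these changes with clinical response as determined by RECIST 1.1". Section 8 repeats both, the second as a plan to "correlate the change of PD-1, PD-L1 levels, immune score, and clonality of the T-cell repertoire from Sylatron treatment with clinical response".

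Section 8.1 provides the matching samples. Each patient has a biopsy within 42 days before treatment "and 3 weeks later prior to initiation of pembrolizumab (prior to Cycle 2 Day 1"). Both biopsies may be omitted where tissue cannot safely be obtained.

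Section 12.4.3 is the only analysis text for these objectives, and it has two parts. CD3 and CD8 density, CD8 proliferation, Granzyme B+ cells and tumour-cell proliferation are listed and summarised by minimum, maximum, mean, median and standard deviation. CD8+ T cells, Granzyme B+ cells and tumour-cell proliferation are then related to response by "comparing the means of different groups using either 2-sample t-tests or non-parametric Wilcoxon rank-sum test", or by a Chi-square test, depending on the data.

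**The concern.** Section 2.1.3 uses the word test for the first step, and the quantity to be tested is a difference between two samples from the same patient. Every test named in 12.4.3 is for independent groups, and none compares the two time points. The second step concerns the change, but 12.4.3 names only the markers. Three markers in the objectives do not appear in 12.4.3.

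What is at stake is the trial's mechanistic argument. The trial has one arm, and its response rate is judged against an external 17%. The three weeks before pembrolizumab are the only scheduled period on Sylatron alone before the combination begins, and the second biopsy is taken to see what happens in them. If 12.4.3 is followed as written, the report will contain summaries of markers and comparisons by response group, but no estimate of how far the markers moved. A method chosen after the data are seen would weaken whatever is then said about mechanism.

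**Working it through.** The documents give no sample size, effect size, variance or power for the biopsy analysis, so there is no figure of the plan's own to reproduce. The check sets the texts side by side.

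**1. Markers.** The objectives are in sections 2.1.3 and 8, the analysis in 12.4.3.

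| Marker in the objectives | Summarised in 12.4.3 | Related to response in 12.4.3 | Change analysed in 12.4.3 |
|---|---|---|---|
| CD3 density | yes | no | not stated |
| CD8 density | yes | CD8+ T cells named; density or proliferation unclear | not stated |
| CD8 proliferation | yes | as above | not stated |
| Granzyme B+ cells | yes | yes | not stated |
| Tumour-cell proliferation | yes | yes | not stated |
| PD-1 | no | no | not stated |
| PD-L1 | no | no | not stated |
| T-cell clonality | no | no | not stated |

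Five of eight are summarised, three terms are related to response, and none has a stated analysis of change. Clonality is listed as an endpoint in sections 2.2.3 and 12.2.3; PD-1 and PD-L1 are not.

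**2. Which variable goes with response.** The second bullet of 2.1.3 and 12.4.3 name largely the same markers, but the bullet says changes and 12.4.3 does not. Section 8 names PD-1, PD-L1, immune score and clonality. The only possible overlap with 12.4.3 is the CD8 part of the immune score.

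**3. Whether the descriptive statistics can stand in.** Suppose they are given separately at baseline and week 3, which 12.4.3 does not say. Two means give a mean difference, but two standard deviations do not give its precision. That depends on the within-patient correlation ρ:

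variance of change = s₀² + s₃² − 2ρs₀s₃; with equal SD s, SD of change = s√(2(1−ρ)).

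The documents give no ρ. Over an assumed range:

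- ρ = 0: √2.0 = 1.41 s
- ρ = 0.3: √1.4 = 1.18 s
- ρ = 0.5: √1.0 = 1.00 s
- ρ = 0.7: √0.6 = 0.77 s

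The same pair of summaries therefore fits intervals that differ in width by 1.18/0.77 = 1.5 between ρ = 0.3 and ρ = 0.7. The change has to be computed per patient.

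**4. Number of pairs.** Section 12.3 plans 44 patients, or 16 if the trial stops at the first stage. Section 8.1 lets both biopsies be omitted, so the number of pairs is unknown.

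**5. What the change measures.** Baseline tissue may be up to 42 days old at Day 1, and the second biopsy comes 21 days later, so the interval can reach 42 + 21 = 63 days. Section 3.2 excludes chemotherapy and radiation only within 14 days before Day 1. A baseline biopsy can therefore precede the last permitted prior treatment by about 42 − 14 = 28 days. There is no control group for this interval.

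**The case against.** The strongest reply is that the sentence quoted from 12.4.3 contains no error. It concerns response groups. Responders and non-responders are different patients, so a 2-sample t, rank-sum or Chi-square test is the right type. Applied to each patient's change, it uses the pairing fully. This stands, and the tests should be kept.

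A reader might infer that the plan compares levels rather than changes with response. The documents do not support that. Section 12.4.3 is silent, and 2.1.3 and 8 both say change. A reader might also infer that the effect of Sylatron is never to be tested. Sections 2.1.3 and 8 commit to a test; what is missing is its method.

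It is also tempting to put a power loss on the omission by setting a signed-rank test against an unpaired rank-sum test of baseline versus week 3. The plan proposes no such unpaired test, and the number of pairs, the shift and the correlation would all be assumed. No such loss is claimed here.

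Finally, the objective is exploratory, with no decision rule attached, so a powered test is not required. That is right and limits the severity. It does not excuse the absence of an estimate: sections 12.4.1 and 12.4.2 give confidence intervals for response, progression-free survival and overall survival, and 12.4.3 gives none for the change.

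**Conclusion.** The point holds as a mismatch between objective and analysis. Sections 2.1.3 and 8 commit to testing a within-patient change and relating it to response. Section 12.4.3 does not define that change, estimate it or analyse it as paired data, and it leaves out three of the eight markers. This follows from the text alone; the correlations in the working only illustrate why separate summaries are not enough.

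The size is minor to moderate. The primary endpoint, the stopping rule and the secondary endpoints are untouched, and the samples are collected in any case.

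A reader might take the paired biopsies to isolate the effect of Sylatron. They cover a period on Sylatron without pembrolizumab, but the contrast is before-after and uncontrolled. The end of prior therapy, elapsed time and differences between tissue samples can all contribute. A paired test would show that a marker changed, not that Sylatron changed it.

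**What to change.** Amend section 12.4.3 as follows.

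1. For CD3 and CD8 density, CD8 proliferation, Granzyme B+ cells, tumour-cell proliferation, PD-1, PD-L1 and clonality, report the per-patient change (week 3 minus baseline, on the log scale where suitable). Give a 95% confidence interval and a paired t or Wilcoxon signed-rank test. If the Low/High score of section 8 is analysed, use McNemar's test with one cut-off for both time points, such as the baseline median. A median taken afresh at each visit would put about half the patients in each class both times and hide any shift.
2. Apply the by-response tests to the change, or to the week-3 value adjusted for baseline. State whether the CD8 term means density, proliferation or both.
3. Use patients with both biopsies, and report how many lack a pair and why.
4. Label the p-values exploratory and unadjusted for multiplicity, and describe the change as an uncontrolled before-after contrast.

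The cost is wording and some analysis time, with no new samples and no change to conduct. The downside is a few more exploratory tests. With CD3 and CD8 density at two sites (4) and the other six markers, there are at least 10 tests of change. At 5% each, 10 × 0.05 = 0.5 false positives would be expected if nothing changed, which is why the label in item 4 is needed.
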